3.8. Assess of Coronavirus Disease 2019 Impact

This study was ongoing during the coronavirus disease 2019 (COVID-19) pandemic.

The assessment on the impact of COVID-19 will be provided in the corresponding sections (eg, Section 4) throughout this SAP. Study drug and study discontinuation due to COVID-19 are described in Section 4.1, study drug interruptions due to COVID-19 are described in Section 4.2, important and non-important protocol deviations due to COVID-19 are described in Section 4.3, and missed and virtual visits due to COVID-19 are described in Section 4.4.

Hematocrit collected from local laboratory and weight measured at home due to COVID-19 impact will be used in CDAI calculations only, and will not be included in the safety laboratory summary (Sections 7.2 and 7.3, respectively). These data will be included in listings, with a flag to indicate which records were collected at a local laboratory or at home, respectively.

4. SUBJECT DISPOSITION

4.1. Subject Enrollment and Disposition

A summary of subject enrollment will be provided by treatment group for each country, investigator within a country, and overall. The summary will present the number and percentage of subjects enrolled. For each column, the denominator for the percentage calculation will be the total number of subjects analyzed for that column.

A similar enrollment table will be provided by randomization stratum. The denominator for the percentage of subjects in the stratum will be the total number of enrolled subjects within that stratum. If there are discrepancies in the value used for stratification assignment between the IWRS and the clinical database, the value collected in the clinical database will be used for the summary. A listing of subjects with discrepancies in the value used for stratification assignment between the IWRS and the clinical database at the time of data finalization will be provided.

The randomization schedule used for the study will be provided as an appendix to the CSR.

A summary of subject disposition will be provided by treatment group and overall. This summary will present the number of subjects screened, the number of subjects who met all eligibility criteria but were not randomized with reasons subjects not randomized, the number of subjects randomized, and the number of subjects in each of the categories listed below:

- All Randomized Analysis Set
- Full Analysis Set
- Safety Analysis Set
- [REDACTED]
- [REDACTED]
- Completed study drug
- Did not complete study drug with reasons for premature discontinuation of study drug
- Completed study
- Did not complete the study with reasons for premature discontinuation of study

For the status of study drug and study completion and reasons for premature discontinuation, the number and percentage of subjects in each category will be provided. The denominator for the percentage calculation will be the total number of subjects in the Safety Analysis Set corresponding to that column.

The following by-subject listings will be provided by subject identification (ID) number in ascending order to support the above summary tables:

- Reasons for premature study drug or study discontinuation (A separate listing of reasons for premature study drug or study discontinuation due to COVID-19 will be created.)
- Reasons for screen failure (will be provided by screening ID number in ascending order)
- Lot number and kit ID of assigned study medication

4.2. Extent of Study Drug Exposure and Adherence

Extent of exposure to study drug will be examined by assessing the total duration of exposure to study drug and the level of adherence to the study drug specified in the protocol. Summaries of extent of study drug exposure and adherence will be provided by treatment group for Safety Analysis Set.

A by-subject listing will be provided for subjects with study drug interruption due to COVID-19.

4.2.1. Duration of Exposure to Study Drug

Total duration of exposure to study drug will be defined as last dosing date minus first dosing date plus 1, regardless of any temporary interruptions in study drug administration, and will be expressed in weeks using up to 1 decimal place (eg, 4.5 weeks). If the last study drug dosing date is missing, the latest date among the study drug end date, clinical visit date, laboratory sample collection date, and vital signs assessment date that occurred during the on-treatment period will be used.

The total duration of exposure to study drug will be summarized using descriptive statistics (n, mean, SD, median, Q1, Q3, minimum, and maximum) and using the number (ie, cumulative counts) and percentage of subjects exposed through the following time periods: Day 1, Weeks 2, 4, 6, 10, 14, 18, 20, and 24. Summaries will be provided by treatment group for the Safety Analysis Set.

No formal statistical testing is planned.

4.2.2. Adherence to Study Drug

The total number of tablets administered will be summarized using descriptive statistics.

The presumed total number of tablets administered to a subject will be determined by the data collected on the drug accountability eCRF using the following formula. If the bottle was not returned, it is assumed that the subject took all the study drug tablets from the dispensed bottle. The number of tablets returned will be imputed as zero for the given bottle for study drug adherence calculation purpose.

$$\begin{aligned} \text{Total Number of Tablets Administered} \\ = \left(\sum \text{No. of Tablets Dispensed} \right) - \left(\sum \text{No. of Tablets Returned} \right) \end{aligned}$$

4.2.2.1. On-Treatment Adherence

The level of on-treatment adherence to the study drug regimen will be determined by the total amount of study drug administered relative to the total amount of study drug expected to be administered during a subject's actual on-treatment period based on the study drug regimen.

The level of on-treatment adherence will be expressed as a percentage using the following formula:

$$\text{On-Treatment Adherence (\%)} = \left(\frac{\text{Total Amount of Study Drug Administered}}{\text{Study Drug Expected to be Administered on Treatment}} \right) \times 100$$

If the calculated on-treatment adherence is > 100%, it will be set to 100%. Descriptive statistics for the level of on-treatment adherence with the number and percentage of subjects belonging to adherence categories (eg, < 80%, ≥ 80% to < 90%, ≥ 90%) will be provided by treatment group for the Safety Analysis Set.

No formal statistical testing is planned.

A by-subject listing of study drug administration and drug accountability will be provided by subject ID number (in ascending order) and visit (in chronological order).

4.3. Protocol Deviations

Subjects who did not meet the eligibility criteria for study entry, but enrolled in the study will be summarized. The summary will present the number and percentage of subjects who did not meet at least 1 eligibility criterion and the number of subjects who did not meet specific criteria by treatment group based on the All Randomized Analysis Set. A by-subject listing will be provided for those subjects who did not meet at least 1 eligibility (inclusion or exclusion) criterion. The listing will present the eligibility criterion (or criteria if more than 1 deviation) that subjects did not meet and related comments, if collected.

Protocol deviations occurring after subjects entered the study are documented during routine monitoring. The number and percentage of subjects with important protocol deviations by deviation category (eg, eligibility criteria, informed consent) will be summarized by treatment group for the All Randomized Analysis Set. A by-subject listing will be provided for subjects with any important protocol deviations.

A by-subject listing will be provided for subjects with important protocol deviations related to COVID-19. A separate listing will be provided for subjects with non-important protocol deviations related to COVID-19.

4.4. Missed and Virtual Visits due to COVID-19

A by-subject listing of subjects with missed or virtual visits due to COVID-19 will be provided by subject ID number in ascending order.

The determination of missing or virtual visits due to COVID-19 was done using Natural Language Processing (NLP) to search the CRF comment fields. A detailed explanation of the algorithm is provided in [Appendix 7](#).

5. BASELINE CHARACTERISTICS

5.1. Demographics and Other Baseline Characteristics

Subject demographic variables and other baseline characteristics will be summarized by treatment group and overall using descriptive statistics for continuous variables and using the number and percentage of subjects for categorical variables. The summary of demographic data will be provided for the Safety Analysis Set.

- Age (years, on the date of first dose of the study drug)
- Age group (< 65 years, \geq 65 years)
- Sex at birth (female, male)
- Race
- Ethnicity (Hispanic or Latino, Not Hispanic or Latino)
- Geographic region (United States [US], non-US)
- Weight
- Height
- Body mass index (BMI; in kg/m²)
- Smoking status (former, current, never)

A by-subject demographic listing, including the informed consent date, will be provided by subject ID number in ascending order.

5.2. Baseline Disease Characteristics

Stratification factors (listed in Section 3.3) and other baseline disease characteristics listed below will be summarized for the Safety Analysis Set by the same method as demographic tables, using descriptive statistics for continuous variables, and using number and percentage of subjects for categorical variables.

- Duration of CD (years) from date of diagnosis to first dosing date of study drug
- Duration of CD (< 1 year, \geq 1 to < 3 years, \geq 3 to < 7 years, \geq 7 years)
- CDAI score
- PRO2 subscores: liquid or very soft stool subscore and abdominal pain subscore

- Active disease in (yes if segmental MaRIA ≥ 7 ; otherwise no)

Terminal ileum

Distal ileum

Jejunum

At least 2 of the following segments: terminal ileum, distal ileum, or jejunum

- Presence of ulcerative lesions in (yes if segmental MaRIA ≥ 11 ; otherwise no)

Terminal ileum

Distal ileum

Jejunum

At least 2 of the following segments: terminal ileum, distal ileum, or jejunum

■ [REDACTED]

■ [REDACTED]

■ [REDACTED]

- Complications of CD: Fistula (yes, no), Stricture (yes, no), Abscess (yes, no)
- History of surgeries due to CD (yes, no)
- CD treatment history

Number of prior exposure to biologic agent as listed in [Appendix 2](#) (0, 1, 2, ≥ 3)

Prior use of systemic corticosteroids (yes, no)

Prior use of immunomodulators (yes, no)

Prior use of TNF α antagonist as listed in [Appendix 2](#) (yes, no) and for subjects with prior use:

- Number of TNF α antagonist used

○ 1

○ 2

○ ≥ 3

- Worst outcome of prior use of TNF α antagonist
 - Treatment failure
 - Intolerance, including both allergic and non-allergic intolerance
 - Other

Prior use of vedolizumab (yes, no) and for subjects with prior use:

- Worst outcome of prior use of vedolizumab
 - Treatment failure
 - Intolerance, including both allergic and non-allergic intolerance
 - Other

Prior use of both TNF α antagonist and vedolizumab (yes, no)

Prior failure of both TNF-alpha antagonist and vedolizumab

- Yes (dual refractory, defined as those who have failed at least 2 classes of biologic therapies [any TNF α antagonist and vedolizumab])
 - United States (US) Males
 - Subjects other than US Males
- No
 - US Males
 - Subjects other than US Males

Prior use of ustekinumab (yes, no) and for subjects with prior use:

- Worst outcome of prior use of ustekinumab
 - Treatment failure
 - Intolerance, including both allergic and non-allergic intolerance
 - Other

Note: The worst outcome of a prior treatment is treatment failure, followed by intolerance, and then other outcomes.

- Concomitant treatment at baseline:

Concomitant use of systemically absorbed corticosteroids and/or immunomodulator at baseline including: a) systemically absorbed corticosteroids only, b) immunomodulator only, c) both, and d) neither

Prednisone equivalent dose for subjects who are on systemically absorbed corticosteroids at baseline (mg/day)

Prednisone equivalent dose for subjects who are on systemically absorbed corticosteroids at baseline (> 0 to 10 mg/day, > 10 to 20 mg/day, > 20 mg/day)

5-aminosalicylates (yes, no)

A by-subject listing of baseline characteristics will be provided by subject ID number in ascending order.

5.3. Medical History

Medical history (disease-specific and general conditions) and IBD family history data will be collected at screening and presented in data listings.

General medical history data will be coded using the current version of Medical Dictionary for Regulatory Activities (MedDRA).

6. EFFICACY ANALYSES

6.1. General Considerations

[figure not shown]
The efficacy analysis will be conducted on the FAS, defined in Section 3.1.2, unless otherwise specified.

The definitions of dichotomous efficacy endpoints are provided in [Table 6-1, Appendix 6](#) includes a detailed definition of study treatment failure and the corresponding data handling rules for efficacy analysis.

Table 6-1. Definitions of Dichotomous Efficacy Endpoints

Type	Endpoint	Definition
Primary	Clinical remission by CDAI at Week 24	CDAI score < 150 points at Week 24
Secondary	MaRIA remission in terminal ileum segment at Week 24	MaRIA score < 7 in terminal ileum segment at Week 24 among subjects with MaRIA score ≥ 7 in the same segment at Baseline
Secondary	MaRIA remission in distal ileum segment at Week 24	MaRIA score < 7 in distal ileum segment at Week 24 among subjects with MaRIA score ≥ 7 in the same segment at Baseline
Secondary	MaRIA remission in jejunum segment at Week 24	MaRIA score < 7 in jejunum segment at Week 24 among subjects with MaRIA score ≥ 7 in the same segment at Baseline
Secondary	MaRIA response in terminal ileum segment at Week 24	Among subjects with Baseline MaRIA score ≥ 7 in terminal ileum: 
if baseline MaRIA score ≥ 11, a segmental MaRIA score < 11, or a decrease from baseline in segmental MaRIA score \geq MDD in terminal ileumif baseline MaRIA score < 11, a segmental MaRIA score < 7, or a decrease from baseline in segmental MaRIA score \geq MDD in terminal ileum
Secondary	MaRIA response in distal ileum segment at Week 24	Among subjects with Baseline MaRIA score ≥ 7 in distal ileum: 
if baseline MaRIA score ≥ 11, a segmental MaRIA score < 11, or a decrease from baseline in segmental MaRIA score \geq MDD in distal ileumif baseline MaRIA score < 11, a segmental MaRIA score < 7, or a decrease from baseline in segmental MaRIA score \geq MDD in distal ileum

Type	Endpoint	Definition
Secondary	MaRIA response in jejunum segment at Week 24	
Among subjects with Baseline MaRIA score ≥ 7 in jejunum:
 
 if baseline MaRIA score ≥ 11, a segmental MaRIA score < 11, or a decrease from baseline in segmental MaRIA score \geq MDD in jejunum if baseline MaRIA score < 11, a segmental MaRIA score < 7, or a decrease from baseline in segmental MaRIA score \geq MDD in jejunum
Secondary	Subject level small bowel MaRIA remission at Week 24	MaRIA score < 7 at Week 24 in each of the 3 small bowel segments: terminal ileum, distal ileum, and jejunum, among subjects with MaRIA score ≥ 7 in at least 1 small bowel segment at Baseline
Secondary	Subject level small bowel MaRIA response at Week 24	All small bowel segments with Baseline MaRIA score ≥ 7 achieve segment level MaRIA response, with no segment level disease worsening in any other segment(s) at Week 24, among subjects with MaRIA score ≥ 7 in at least 1 small bowel segment at Baseline
Secondary	Early Clinical remission by CDAI at Week 10	CDAI score < 150 points at Week 10

Summary of Dichotomous Efficacy Endpoints

Numbers and percentages of subjects achieving each of the dichotomous efficacy endpoints defined above, and numbers and percentages of subjects not achieving those endpoints for the following reasons will be summarized by treatment, in a hierarchy order with the first reason being the highest.

- 1) Subjects who do not meet the endpoint based on observed data
- 2) Subjects who do not meet the endpoint due to study treatment failure
- 3) Subjects who are protocol-specified CDAI non-responders at Week 10 and discontinued study drug

- 4) Subjects who do not meet the endpoint due to study drug discontinuation led by protocol-specified disease worsening
- 5) Subjects who do not have sufficient measurements to determine the endpoint due to study drug discontinuation for other reasons
- 6) Subjects who do not have sufficient measurements to determine the endpoint while on study drug

Non-Responder Imputation

For analysis of binary efficacy endpoints defined in [Table 6-1](#), subjects who do not have sufficient measurements due to any reason (including treatment failures and CDAI non-responders at Week 10) to determine the endpoint will be considered non-responders (ie, non-responder imputation [NRI]).

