#### **6.5. Magnetic Resonance Enterography**

A centrally read MRE will be conducted at screening and Week 24 to characterize the disease extent and response to filgotinib treatment in subjects with SBCD.

Screening MRE should be performed only after subject eligibility based on CDAI is confirmed. If there are any outstanding screening clinical laboratory assessments at the time the baseline CDAI is calculated, these results must also be confirmed as being within eligibility requirements prior to conducting the MRE. Consideration should be given to central reader review turnaround times to ensure results are available prior to Day 1. Screening MRE may not be repeated.

Week 24 MRE should be performed 7 to 14 days prior to the Week 24 visit. Glomerular filtration rate (GFR) using the Cockcroft-Gault Model for creatinine clearance from the Week 18 visit should be reviewed prior to the Week 24 MRE. Since this procedure involves the use of a gadolinium-based contrast, subjects with an eGFR < 40 mL/min at Week 18 require approval from the Medical Monitor to undergo MRE.

For additional details on the MRE procedure, refer to the MRE Manual.

CC1

[figure not shown]
[figure not shown]
[figure not shown]
[figure not shown]
[figure not shown]
[figure not shown]
[figure not shown]
[figure not shown]
[figure not shown]
[figure not shown]
[figure not shown]
[REDACTED]

[REDACTED]

[REDACTED]

[REDACTED]

CCI

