Disease Worsening	A \geq 100 point increase in CDAI score from the Week 10 value and CDAI score \geq 220 points at 2 consecutive visits
Non-responder	Subjects who never achieves a \geq 70 point CDAI reduction from baseline or CDAI < 150 at any point up to and including Week 10
Minimal Detectable Difference (MDD) by MRE	For segments with baseline MaRIA score \geq 15, the MDD is 6.5 units. For segments with baseline MaRIA score < 15, the MDD is 4.0 units.
Segment with Active Disease	Segmental MaRIA score \geq 7
Segment with Presence of Ulcerative Lesions (Moderate to Severe Radiographic Disease Activity)	Segmental MaRIA score \geq 11
Segment with Mild Radiographic Disease Activity	Segmental MaRIA score \geq 7 but < 11
Segment Level MaRIA Remission	For segments with baseline MaRIA score \geq 7, a segmental MaRIA score < 7 at Week 24
Segment Level MaRIA Response	For segments with baseline MaRIA score \geq 11, a segmental MaRIA score < 11, or a decrease from baseline in segmental MaRIA score \geq MDD For segments with baseline MaRIA score < 11 (but \geq 7), a segmental MaRIA score < 7 or a decrease from baseline in segmental MaRIA score \geq MDD
Segment Level Disease Stable	For segments with baseline MaRIA score \geq 7, absence of segment level MaRIA response and: if baseline MaRIA score \geq 11, no increase in segmental MaRIA score \geq MDD if baseline MaRIA score < 11, a segmental MaRIA score < 11 For segments with baseline MaRIA score < 7, no segment level disease worsening
Segment Level Disease Worsening	An increase in segmental MaRIA \geq MDD with a segmental MaRIA score \geq 7 at Week 24, or a segmental MaRIA score \geq 11 at Week 24 while baseline MaRIA score < 11
Subject Level Small Bowel MaRIA Remission	MaRIA score of < 7 in each of 3 segments: terminal ileum = distal 15 cm of ileum, measured from ileocecal valve distal ileum = the portion of the ileum proximal to terminal ileum jejunum = small bowel located at the left upper quadrant
Subject Level Small Bowel MaRIA Response	All small bowel segments with baseline MaRIA score \geq 7 achieve segment level MaRIA response, with no segment level disease worsening in any other segment(s)
Subject with Stable Small Bowel Disease	At least 1 small bowel segment with baseline MaRIA score \geq 7 doesn't achieve segment level response, while no segment level disease worsening in any other evaluable small bowel segment(s)

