6.1.2. Calculation of MaRIA Scores and Corresponding Endpoints

The MaRIA scoring system is a composite index of 4 components. These components are edema, ulcers, gut wall thickness, and relative contrast enhancement (RCE). A segmental MaRIA score can be calculated at Screening (used as the baseline) and Week 24 as a weighted sum of these 4 components for each of the 3 small bowel segments (terminal ileum, jejunum, and duodenum).

For segment level remission or response based on MaRIA score, if a bowel segment that was identified at baseline has a segmental MaRIA score missing at Week 24, no imputation will be done and the subject will be considered as having insufficient data to determine segment level remission or response status and treated as a non-responder in that specific segment.

For subject level remission or response based on MaRIA score, if more than one small bowel segment that was identified at baseline is missing at Week 24, the subject will be considered as having insufficient data to determine remission or response status and will be considered as a non-responder. If only one small bowel segment that was identified at baseline is missing at Week 24, then LOCF will be used to impute the missing segment. Small bowel segments with missing segmental MaRIA scores at baseline will not be considered when assessing subject level response status.

Detailed information on MaRIA score calculation rules are provided in [Appendix 5](#).

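### Subject-level MaRIA remission needs all three segments below 7, and the SAP does not settle how a segment with no score at either visit counts

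*SAP*

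**What the plan says.** Table 6-1 in SAP 6.1 requires, for subject-level remission, "MaRIA score < 7 at Week 24 in each of the 3 small bowel segments: terminal ileum, distal ileum, and jejunum". The endpoint is confined to those who enter with active small bowel disease: "among subjects with MaRIA score ≥ 7 in at least 1 small bowel segment at Baseline". The Definition of Terms in the SAP and in the protocol sets the same three-segment condition, and neither limits it to evaluable segments. The protocol's definition of subject-level response does carry that limit.

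Missing segments are handled in SAP 6.1.2. The subject-level paragraph opens with both endpoints: "For subject level remission or response based on MaRIA score, if more than one small bowel segment that was identified at baseline is missing". When this happens for the Week 24 scan, the consequence is non-responder status. It continues: "If only one small bowel segment that was identified at baseline is missing at Week 24, then LOCF will be used". It closes with the rule for baseline gaps: "Small bowel segments with missing segmental MaRIA scores at baseline will not be considered when assessing subject level response status". That last sentence does not name remission.

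SAP 6.1 also applies a general non-responder imputation to anyone whose data are too incomplete, for whatever cause, to determine a binary endpoint.

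**The concern.** Eligibility needs a score of 7 or more in only one of the three segments, so a subject can be enrolled with another segment unscored. Two routes are plausible. Prior ileocecal resection is not among the exclusions: exclusion 19 names colectomy and stoma, and exclusion 16 covers only major surgery or trauma in the 30 days before screening. SAP 5.2 tabulates past surgery for Crohn's disease, and the SAP locates one segment by a landmark that resection removes: "terminal ileum = distal 15 cm of ileum, measured from ileocecal valve". The other route is image quality. Protocol 6.5 says "Screening MRE may not be repeated", so a baseline gap stays a gap, and the same segment may be unreadable again at Week 24.

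If such a subject is a remission failure by definition, a feature fixed before randomisation is counted as treatment failure on a named secondary endpoint. That lowers the rate in every arm, and with only 20 placebo subjects a chance imbalance in the number affected could move the comparison either way.

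**Working it through.** **The plan's own figure.** SAP 1.3 gives a 90% exact interval of 26.9% to 54.2% for a 40% rate with 40 subjects. Clopper-Pearson limits for 16/40 are the 5% quantile of Beta(16, 25) = 26.94% and the 95% quantile of Beta(17, 24) = 54.22%, so it reproduces. It concerns CDAI remission. The documents give no design figure for MaRIA remission.

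**Step 1: apply the rules to cases.** Scores are illustrative, in the order terminal ileum, distal ileum, jejunum; a dash means no score.

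| Case | Baseline | Week 24 | Table 6-1 read literally | Baseline-gap rule extended to remission |
|---|---|---|---|---|
| A. Unscored at both visits | –, 12, 5 | –, 5, 5 | not a remitter | remitter |
| B. Unscored at baseline, then below 7 | –, 12, 5 | 5, 5, 5 | remitter | remitter |
| C. Unscored at baseline, then 7 or more | –, 12, 5 | 9, 5, 5 | not a remitter | remitter |
| D. Scored below 7 at baseline, missing at Week 24 | 12, 5, 5 | 5, –, 5 | remitter (LOCF gives 5) | remitter |

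- Case A is the only one that fails whatever happens in the scorable segments, and only on the literal reading. LOCF cannot help, because it applies only to segments identified at baseline.
- The subject in case A is a subject-level responder. The distal ileum starts at 12 (11 or more) and ends at 5 (below 11), the jejunum does not worsen, and the terminal ileum is set aside.
- Cases A and D are treated inconsistently. A segment seen once and then missed can be carried forward to remission; a segment never scored cannot.
- Cases A and C change result with the reading chosen.

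**Step 2: size on the literal reading.** Let q be the share of subjects with a segment unscored at both visits. The highest attainable rate is 1 − q. Suppose the remission rate p, counting scorable segments only, is the same in affected and unaffected subjects and q is equal across arms. Then the observed rate is p(1 − q) and the observed difference is (p1 − p0)(1 − q). The documents give neither q nor p; the values below are assumptions, with p1 = 30% and p0 = 15%.

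| q | Ceiling | Active | Placebo | Difference |
|---|---|---|---|---|
| 0% | 100% | 30.0% | 15.0% | 15.0 points |
| 10% | 90% | 27.0% | 13.5% | 0.15 × 0.90 = 13.5 points |
| 20% | 80% | 24.0% | 12.0% | 0.15 × 0.80 = 12.0 points |
| 30% | 70% | 21.0% | 10.5% | 0.15 × 0.70 = 10.5 points |

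If every segment unscored at baseline is read at Week 24, q is 0 and nothing shrinks.

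**Step 3: imbalance.** One affected subject takes 1/20 = 5 points off the placebo ceiling, or 1/40 = 2.5 points off a filgotinib ceiling, at the planned group sizes.

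**The case against.** The best defence is that the SAP already has a rule for baseline gaps. It sits in a paragraph that opens with both endpoints, and the SAP uses response vocabulary loosely: the CDAI missing-data text in 6.1.1 speaks of response status although the listed binary CDAI endpoints are remission, and subjects who miss remission are called non-responders. The more-than-one-missing rule in 6.1.2 also counts only segments identified at baseline, so it does not itself fail the subject in case A; that takes the general imputation rule plus the narrow reading. This stands as far as it goes: the scope of the sentence is ambiguous, not plainly limited. It does not remove the problem. Elsewhere in 6.1.2, where both endpoints are meant, both are named, and the generous reading sets 6.1.2 against Table 6-1.

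A reader might infer that any segment unreadable at baseline makes the subject a non-remitter whatever the drug does. The documents do not support that, because remission is decided on Week 24 scores (case B). A reader might also infer that past surgery means a missing terminal ileum. The surgery item does not identify ileocecal resection, and how the central readers label remaining ileum may be set out in the MRE Manual, which is not available here.

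Finally, this is one of 14 secondary endpoints with no formal testing, and the planned table of reasons for not achieving each endpoint gives some visibility. Both points lower the priority.

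**Conclusion.** The concern holds for a segment with no score at either visit. Literally applied, the plan makes that subject a certain remission failure while allowing a response; generously applied, 6.1.2 and Table 6-1 give opposite answers. Either way the text needs reconciling before programming.

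The size cannot be fixed from the documents. An assumed q of 10% to 30% takes an assumed 15-point difference to 13.5 to 10.5 points, provided q and the underlying remission rate do not depend on arm or on having such a segment, respectively. The ceiling of 1 − q needs neither condition. The primary endpoint, the sample size and error control are untouched. Priority is low to moderate.

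**What to change.** - In Table 6-1, the SAP Definition of Terms and 6.1.2, define subject-level remission as a Week 24 score below 7 in every small bowel segment with a baseline score (at least one of them 7 or more), and in any other segment scored at Week 24. A segment with no score at either visit is not counted. Keep the existing rules for segments missing at Week 24.
- Put this in 6.1.2 as a separate sentence on remission. Simply extending the existing baseline-gap sentence would also ignore a segment unscored at baseline and active at Week 24 (case C), which the definition above correctly counts.
- Reconcile the segment list in 6.1.2, which has duodenum where Table 6-1 has distal ileum; it determines which segments count.
- List the departure from the protocol definition in SAP 6.5.
- Tabulate by arm the subjects with fewer than three scored segments, at baseline and at both visits.

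The cost is SAP wording and one small table, before database finalization. The downside is that remission rests on fewer segments for the affected subjects, so the endpoint is slightly more lenient for them; the table shows how many there are.

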### **8.5. Efficacy Analysis**

#### **8.5.1. Primary Analysis**

For the primary efficacy endpoint, the number and proportion of subjects achieving clinical remission at Week 24 for each treatment group will be summarized with corresponding 90% exact confidence interval (CI) based on the binomial distribution (Clopper-Pearson method). The difference in proportions between each filgotinib dose group and the placebo group will be presented along with the associated 90% CI. Subjects who do not have sufficient measurements to determine efficacy endpoints will be considered failures (ie, non-responder imputation [NRI]). No formal hypothesis testing will be performed.

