1.3. Sample Size and Power

A sample size of 40 subjects in each of the filgotinib treatment groups and 20 subjects in the placebo group is considered adequate to assess the safety, tolerability, and efficacy of filgotinib in a descriptive manner. Assuming a clinical remission rate of 40% for the filgotinib treatment groups (200 mg and 100 mg), the 2-sided 90% exact confidence interval is (26.9%, 54.2%). The clinical remission rate for placebo group is assumed to be 20%.

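### Binary endpoint results lost only to COVID-19 are scored as non-response, and no supplementary analysis shows the effect; the MaRIA endpoints are the most exposed

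*SAP*

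**What the plan says.** SAP section 6.1 applies non-responder imputation (NRI) to every binary endpoint in Table 6-1, covering "subjects who do not have sufficient measurements due to any reason (including treatment failures and CDAI non-responders at Week 10) to determine the endpoint". Protocol section 8.5.1 has the same rule: "Subjects who do not have sufficient measurements to determine efficacy endpoints will be considered failures". Neither makes an exception for the pandemic.

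SAP section 3.8 states: "This study was ongoing during the coronavirus disease 2019 (COVID-19) pandemic". Appendix 7 sets out an algorithm that searches CRF comments to label visits as missed or virtual because of COVID-19. Section 4.4 gives its use: "A by-subject listing of subjects with missed or virtual visits due to COVID-19 will be provided by subject ID number in ascending order". In the readable text, neither the primary analysis (6.2.2) nor the secondary analyses (6.3.2) refer to that label.

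Section 6.1 also tabulates, by arm, six reasons for not meeting an endpoint. Category 5 is insufficient data after stopping drug for other reasons. Category 6 is insufficient data while still on drug. Neither is split by COVID-19.

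**The concern.** The objective is the efficacy of filgotinib against placebo. A subject who is on drug and doing well, but whose clinic or scanner was closed, is counted as not in remission. That missingness carries no information about the drug, yet it is converted into failure, always in the same direction within an arm. The trial plans no hypothesis test, so the estimated proportions, differences and 90% intervals are the result. A reader of the planned tables could not tell how much of a low rate reflects treatment and how much reflects closed sites.

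**Working it through.** **Inputs.** SAP section 1.3 gives 40, 40 and 20 subjects, 40% remission on each filgotinib dose and 20% on placebo. No document gives the share of results lost to COVID-19. Let m be the share of would-be remitters whose result is lost only to COVID-19. Values of 5% to 20% are assumed.

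**The plan's own figure.** The Clopper-Pearson 90% interval for 16/40 is 26.94% to 54.22%, which matches the stated 26.9% to 54.2%.

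**Equal proportional loss.** The expected rate under NRI is p(1 - m), so the expected difference is (0.40 - 0.20)(1 - m).

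| m | Filgotinib | Placebo | Difference (points) |
|---|---|---|---|
| 0 | 40% | 20% | 20 |
| 5% | 38% | 19% | 19 |
| 10% | 36% | 18% | 18 |
| 20% | 32% | 16% | 16 |

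**Unequal loss.** With m1 on filgotinib and m0 on placebo, the difference is 0.40(1 - m1) - 0.20(1 - m0). It falls below 20 points only if m0 < 2 × m1.

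- 10% and 0%: 36 - 20 = 16 points
- 5% and 10%: 38 - 18 = 20 points
- 0% and 10%: 40 - 18 = 22 points

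In whole subjects, one lost remitter is worth 1/20 = 5 points on placebo and 1/40 = 2.5 points on a filgotinib dose. Starting from 16/40 and 4/20, losing one in each arm gives 37.5% - 15% = 22.5 points.

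**Scale.** The SAP names no interval method for the difference. A Wald 90% half-width with no loss is 1.645 × √(0.24/40 + 0.16/20) = 19.5 points.

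**Which endpoints are exposed.**

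- *CDAI.* Sections 3.8 and 6.1.1 accept home weight and local hematocrit and carry forward one or two missing components. The Week 24 window runs from Day 142 to Day 197. A virtual or postponed visit can therefore usually still yield a score. A fully missed visit cannot: under Appendix 3 the visit date anchors the 10-day diary window, so completed diary entries have nothing to attach to.
- *MaRIA.* A virtual visit cannot supply a scan. Section 6.1.2 scores a segment missing at Week 24 as non-response for that segment. At subject level, more than one missing segment is non-response. A single missing segment is carried forward, which for a segment scoring 7 or more at baseline again gives neither remission nor response.

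**What the COVID-19 label covers.** Appendix 7 labels visits. It returns a missed visit only if the visit date is absent, and a virtual visit only if a virtual term is found. Protocol section 6.5 places the Week 24 MRE 7 to 14 days before the visit. A cancelled scan followed by an attended visit gets neither label.

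**What removing affected subjects would recover.** Suppose only subjects on drug and not already failures are removed. Let d be the share who had already discontinued or failed, let m be the loss among the rest, and assume all would-be remitters are among the rest. The rate becomes p(1 - m)/(1 - m(1 - d)). With m = 10% and assumed d of 40% on filgotinib and 60% on placebo:

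- filgotinib: 0.36/0.94 = 38.3%
- placebo: 0.18/0.96 = 18.75%
- difference: about 19.5 points, against 18 under NRI and 20 with no loss

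**The case against.** NRI is prespecified consistently in both documents, the trial is descriptive, and an assumed bias of 1 to 4 points is small beside a half-width of 19.5. The primary endpoint is largely protected by the CDAI fallbacks. Category 6 together with the COVID-19 listing already lets a reader put a rough bound on the effect.

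Most of this stands, and it limits the size of the point. It does not close the gap. Imprecision does not excuse an avoidable one-directional bias in the arm rates. The fallbacks do nothing for MaRIA. The listing misses cancelled scans when the visit itself was attended.

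A reader might infer more than the documents support:

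- *That the drug-placebo difference must shrink.* This is an expectation under equal proportional loss. With 20 placebo subjects, one or two losses can decide the direction.
- *That the primary endpoint is as exposed as the imaging endpoints.* It is not, for the reasons above.
- *That the figures above size the MaRIA effect.* They rest on CDAI rates; the documents give no MaRIA rates.

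**Conclusion.** The point holds in a limited form. The plan scores results lost only to COVID-19 as non-response, and the readable text has no analysis that shows the effect. Arm-level remission and response rates can only go down. The expected difference on the primary endpoint falls to 19, 18 or 16 points at 5%, 10% or 20% loss, given the plan's 40% and 20% and equal proportional loss. The loss shares are assumptions. If no results were lost this way, nothing changes. The CDAI is exposed mainly through fully missed visits. The MaRIA endpoints are the most exposed, by an amount that cannot be derived from the documents. No power or type I error is at issue, and NRI itself is not wrong as the main analysis.

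**What to change.** Keep NRI as the main analysis. In SAP section 6.1:

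1. For the primary and each binary secondary endpoint, add a supplementary analysis that removes from the denominator subjects who were on study drug, were not treatment failures, and whose CDAI or MRE at the endpoint visit is missing solely because of COVID-19. All other missing results stay non-response. Report the same proportions, differences and 90% intervals.
2. Decide attribution before unblinding, separately for the CDAI visit and the MRE. Review every CRF comment with COVIDFL = 1 and every missing Week 24 MRE, not only visits labelled missed or virtual by Appendix 7.
3. Split reason categories 5 and 6 by COVID-19.
4. State that the analysis reduces the bias without fully removing it, because subjects who had already discontinued or failed stay in the denominator.

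The cost is SAP wording, one blinded review and one extra table per endpoint. The downside is slightly fewer subjects and reliance on comment-based attribution. The SAP is to be final before the database is, so the rule can still be set in advance; added after unblinding, it would be post hoc.
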